**Table 10-7: Definitions of markedly abnormal hematology values**

Variable (SI Units)	Markedly Abnormal Definition	
	Low	High
Hemoglobin (g/L)	<80	>40 above ULN
Lymphocytes (10  /L)	<0.5	>20.0
Neutrophils (10  /L)	<1.0 a	N/A
Platelets (10  /L)	<50	N/A
Leukocytes (10  /L)	<2.0	>100

N/A=not applicable; ULN=upper limit of normal

Data source: modified from Appendix Rheumatology Common Toxicity Criteria v.2.0 presented in Woodworth et al, 2007

a Withdrawal criteria for neutrophils is <0.5.

**Table 10-8: Definitions of markedly abnormal biochemistry values**

Variable (SI Units)	Markedly Abnormal Definition	
	Low	High
ALP	N/A	>5.0 x ULN

**Table 10–8: Definitions of markedly abnormal biochemistry values**

Variable (SI Units)	Markedly Abnormal Definition	
	Low	High
ALT	N/A	>5.0 x ULN
AST	N/A	>5.0 x ULN
Total bilirubin	N/A	>3.0 x ULN
GGT	N/A	>5.0 x ULN
Creatinine	N/A	>3.0 x ULN
Glucose (mmol/L)	<1.7	>13.9
Calcium (mmol/L)	<1.75	>3.1
Magnesium (mmo/L)	<0.4	>1.23
Potassium (mmol/L)	<3.0	>6.0
Sodium (mmol/L)	<130	>155
Total cholesterol (mmol/L)	N/A	>10.34

ALP=alkaline phosphatase; ALT=alanine aminotransferase; AST=aspartate aminotransferase; GGT=gamma glutamyl transferase; N/A=Not applicable; ULN=upper limit of normal.

A summary of the number and percentage of subjects with a given Common Terminology Criteria for Adverse Events (CTCAE) grade (0, 1, 2, 3 or 4) based on minimum/maximum on-treatment value in PA0009 (excluding any measurements that occurred prior to the first administration of study medication in PA0009 or more than 140 days after the last administration of study medication), will be presented by laboratory variable and treatment group at completion of PA0008. This summary will be provided only for selected laboratory variables. Definitions of CTCAE grades are given in [Table 10–9](#) and [Table 10–10](#).

A shift table of the number and percentage of subjects experiencing CTCAE grade 0, 1, 2, 3 or 4 values (as applicable) at PA0009 Laboratory Baseline to minimum/maximum post-PA0009 Laboratory Baseline CTCAE grade will be presented by laboratory variable and treatment group at completion of PA0008. The minimum/maximum post-PA0009 Laboratory Baseline CTCAE grade will include all on-treatment scheduled and unscheduled assessments (excluding any measurements that occurred prior to the first administration of study medication in PA0009 or more than 140 days after the last administration of study medication).

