9. Subject develops laboratory abnormalities (with or without clinical symptoms) of alanine aminotransferase (ALT) or aspartate aminotransferase (AST) as defined in [Section 6.3.1](#); neutrophils $<0.5 \times 10^9/L$ (neutropenia); lymphocytes $<0.5 \times 10^9/L$ (lymphopenia). Any laboratory value or change judged to be clinically significant by the Investigator should prompt consideration of whether the subject should continue on the investigational medicinal product (IMP). For clarification, laboratory values that are markedly abnormal as per [Table 17-1](#) and [Table 17-2](#) will be flagged to the Investigator and to the medical monitor but do not trigger mandatory withdrawal unless listed above. (Refer to [Section 6.3.1](#) for withdrawal criteria in relation to potential drug-induced liver injury [PDILI].)
10. Subject has active suicidal ideation as indicated by a positive response (“Yes”) to Questions 4 or 5 or to the suicidal behavior questions of the “Since Last Visit” version of the self-rated electronic Columbia-Suicide Severity Rating Scale (eC-SSRS). The subject should be referred immediately to a Mental Healthcare Professional and must be withdrawn from the study.
11. Subjects with a HADS-D score ≥ 15 must be withdrawn. Any subject who develops a HADS-D score of >10 during the study should be referred immediately to a Mental Healthcare Professional for further evaluation and potential withdrawal by the Investigator.
12. Subjects with newly diagnosed inflammatory bowel disease (IBD) or with IBD flares during the study must:
 - Be referred, as appropriate, to a health care professional treating IBD, such as a gastroenterologist
 - Discontinue IMP and be followed-up until resolution of active IBD symptoms

If IBD flares increase in severity or frequency during the study, the Investigator should use clinical judgment in deciding whether the subject should continue in the study and contact the Medical Monitor and UCB study physician to confirm the subject's suitability for continued participation in the study.

All subjects who withdraw from the study due to an AE must be followed until resolution of the event or until the event is considered stable. All subjects who withdraw from the study due to development of a laboratory abnormality must be closely monitored.

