17 APPENDICES

17.1 Markedly abnormal laboratory values

Table 17-1: Definitions of markedly abnormal hematology values

Parameter (RCTC units)	Markedly Abnormal Definition	
	Low	High
Hemoglobin (g/dL)	<LLN AND >2.0 decrease from Baseline	N/A
Hemoglobin (g/dL)	<8.0	N/A
Leukocytes (total x 1000)	<2.0	N/A
Lymphocytes (x 1000)	<0.5	N/A
Neutrophils (x 1000)	<1.0 ^a	N/A
Platelets (x 1000)	<50	N/A

LLN=lower limit of normal; N/A = Not Applicable; RCTC= Rheumatology Common Toxicity Criteria
Data source: modified from Appendix Rheumatology Common Toxicity Criteria v.2.0 presented in
Woodworth et al, 2007

^a Withdrawal criteria for neutrophils is <0.5 (Section 6.3)

Table 17–2: Definitions of markedly abnormal biochemistry values

Parameter (RCTC units)	Markedly Abnormal Definition	
	Low	High
Alkaline Phosphatase	N/A	>3 x ULN
ALT	N/A	>3 x ULN
AST	N/A	>3 x ULN
Calcium (mg/dL)	<7.0	>12.5
Creatinine (mg/dL)	N/A	>1.8 x ULN
Glucose (mg/dL)	<40	>250
Potassium (mmol/L)	<3.0	>6.4
Sodium (mmol/L)	<125	N/A
Total bilirubin	N/A	≥2 x ULN
Uric acid	N/A	≥3 x ULN

ALT=alanine aminotransferase; AST=aspartate aminotransferase; N/A=Not applicable; RCTC= Rheumatology
Common Toxicity Criteria; ULN=upper limit of normal

Data source: modified from Appendix Rheumatology Common Toxicity Criteria v.2.0 presented in
Woodworth et al, 2007

17.2 Protocol Amendment 1

Rationale for the amendment

The purpose of this amendment is the following:

- To provide clarification that ACR and PASI responses are compared to both Baseline of PA0008 and PA0009 entry values.
- To correct language regarding administration of live, inactivated vaccinations.
- To remove inclusion of a Data Monitoring Committee.
- To clarify guidance for Investigators when scoring injected joints.

Modifications and changes

Global changes

No global changes have been made. Specific changes are listed below.

Specific changes

Change #1

List of Abbreviations

The following abbreviation has been deleted:

DMC Data Monitoring Committee

Change #2

Summary, paragraph 6, sentence 2

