### 3.10 Changes to protocol-defined analyses

The following changes have been made to the protocol-defined analyses:

- Summaries of ACR20, ACR50, ACR70, PASI75, PASI90, and PASI100 response at each post-PA0008 Baseline visit have been added for subjects who were responders at PA0008 Week 12. These summaries include all post-Baseline PA0008 visits through to PA0009 Week 104 and will be used to assess maintenance of response.
- Summaries of BSA at each visit in PA0009 have been added as an additional method of assessing response in order to provide information at visits where the PASI data may be missing.
- Summaries by randomized treatment in PA0008 will not be produced, as subjects will have been on a constant dose of bimekizumab 160mg or 320mg for at least 36 weeks prior to PA0009 entry. Maintenance of response displays will be split by treatment sequence across PA0008 and PA0009. Safety displays using PA0008 information will incorporate exposure in PA0008.
- The protocol stated that all safety analyses would be performed for both SS Sub-populations; instead only key safety analyses will be repeated by SS Sub-population as identified in [Section 10](#). These analyses will be performed only in the event that the number of subjects receiving rescue medication is  $\geq 10\%$  of the total number of subjects in the SS.
- The protocol stated that figures presenting the relationship between ACR20 response and ADAb positivity over time would be produced. This has been changed to use the ACR50 response instead as this is considered to be the key efficacy endpoint with respect to ACR.

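### The protocol and the SAP use the label markedly abnormal for different laboratory limits, and the SAP does not say so; a few protocol thresholds are left without a count

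*SAP*

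**What the plan says.** Protocol 17.1 (Tables 17-1 and 17-2) defines markedly abnormal hematology and biochemistry values. Protocol 6.3 gives those tables an operational role: values that meet them "will be flagged to the Investigator and to the medical monitor but do not trigger mandatory withdrawal unless listed above".

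SAP 10.3 plans a table of the number and percentage of subjects with at least one on-treatment markedly abnormal value. It uses the definitions in SAP Tables 10-7 and 10-8, the second of which has the same title as the protocol's table: "Definitions of markedly abnormal biochemistry values". The contents differ. For alkaline phosphatase (ALP) the protocol row reads "Alkaline Phosphatase N/A >3 x ULN" and the SAP row "ALP N/A >5.0 x ULN". For bilirubin they read "Total bilirubin N/A ≥2 x ULN" and "Total bilirubin N/A >3.0 x ULN".

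SAP 3.10 opens with "The following changes have been made to the protocol-defined analyses" and lists five items, none about laboratory limits. The log for SAP Amendment 1 mentions added CTCAE summaries and, in general terms, alignment with program conventions. It does not mention these limits.

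**The concern.** Long-term safety is the primary objective, and liver enzyme changes are among the safety topics named in protocol 9.1.3. During the study, a value that meets Table 17-1 or 17-2 is brought to the attention of the investigator and medical monitor as markedly abnormal. A reader of the study report will see a table under the same label and will naturally assume that it counts the same events. Where the SAP limit is looser or missing, it does not. At stake is whether the reported incidence can be read against what was flagged during the study, and whether some flagged abnormalities appear in any summary count.

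**Working it through.** **Inputs.** The limits in protocol Tables 17-1 and 17-2 and in SAP Tables 10-7 and 10-8. The protocol has 6 hematology and 13 biochemistry limits, 6 + 13 = 19, counting low and high sides separately.

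**Unit conversion.** The molar masses are standard values, not figures from the documents.
- Glucose, mg/dL x 10 / 180.156: 40 gives 2.22 mmol/L; 250 gives 13.88 mmol/L.
- Calcium, mg/dL x 10 / 40.078: 7.0 gives 1.747 mmol/L; 12.5 gives 3.119 mmol/L.
- Hemoglobin, g/dL x 10: 8.0 gives 80 g/L.

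**Limits that differ.**

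| Limit | Protocol | SAP | Direction |
|---|---|---|---|
| ALP | >3 x ULN | >5 x ULN | looser |
| ALT | >3 x ULN | >5 x ULN | looser |
| AST | >3 x ULN | >5 x ULN | looser |
| Total bilirubin | ≥2 x ULN | >3 x ULN | looser |
| Creatinine | >1.8 x ULN | >3 x ULN | looser |
| Low glucose | <2.22 mmol/L | <1.7 mmol/L | looser |
| Uric acid | ≥3 x ULN | no row | dropped |
| Hemoglobin fall | <LLN and fall >2.0 g/dL | no row | dropped |
| High potassium | >6.4 mmol/L | >6.0 mmol/L | tighter |
| Low sodium | <125 mmol/L | <130 mmol/L | tighter |

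**Limits that agree after conversion and rounding (9).** Hemoglobin <80 g/L, leukocytes, lymphocytes, neutrophils, platelets, low and high calcium, high glucose, low potassium.

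**Tally.** 9 unchanged (9/19 = 47.4%), 6 looser (31.6%), 2 dropped (10.5%), 2 tighter (10.5%). Looser or dropped: 8 of the 10 altered limits, 7 of the 13 biochemistry limits, 8 of all 19. The SAP adds 8 limits: high hemoglobin, lymphocytes and leukocytes (3), plus high GGT, low and high magnesium, high sodium and high cholesterol (5). The SAP total is 19 - 2 + 8 = 25.

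**Are the 8 looser or dropped limits counted elsewhere in SAP 10.3?**
- ALT and AST: yes. The liver-test table has a >3 x ULN category.
- Bilirubin: yes, at >2 x ULN. Only a value of exactly 2 x ULN is missed.
- Creatinine: in part. Any value above 1.8 x ULN is CTCAE grade 2 (above 1.5, up to 3.0 x ULN) or higher, but 1.8 is not a boundary.
- Hemoglobin fall: in part. A subject below LLN is counted in a CTCAE grade, and the shift table shows changes of grade. The bands are absolute, so someone who just crosses LLN and someone who falls by more than 20 g/L to the same value get the same grade.
- ALP above 3 and up to 5 x ULN: no. It has no CTCAE row and no liver-test category, and enters the Hy's Law criterion only as an exclusion.
- Glucose from 1.7 to below 2.22 mmol/L: no CTCAE row.
- Uric acid ≥3 x ULN: no row in any threshold table.

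**Where the SAP limits come from.** For 18 of the 25, SAP Tables 10-9 and 10-10 grade the same analyte in the same direction, and all 18 equal the CTCAE grade 3 cut-point. The other 7 (ALP, ALT, AST, bilirubin, GGT, low and high glucose) have no row there.

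**The case against.** The strongest reply is that no analysis planned in the protocol has been altered. Protocol 4.3.1 and 13.3.1 plan changes from PA0009 Laboratory Baseline summarized by visit. They plan no incidence table of markedly abnormal values; the SAP added it. The protocol tables serve to flag values during the study, and the SAP leaves that untouched. The SAP limits also look like a coherent grade 3 scheme, which would explain why some limits move in each direction and why 8 are new. No primary or secondary variable depends on these tables. Every analyte is summarized by visit with minimum and maximum, and every value is listed.

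Most of this stands, and it rules out three stronger readings that a reader might infer. One is that the SAP breaches a planned analysis; protocol 13.3.1 does not support that. Another is that protocol-defined abnormalities in general go uncounted; the liver-test and CTCAE tables show otherwise for ALT, AST, bilirubin and, in part, creatinine and hemoglobin. The third is that limits were relaxed to make the safety profile look better; the tighter and added limits and the match with grade 3 argue against it, and the documents give no sign of it.

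The reply does not remove the mismatch of labels. Listings are a weak substitute for a count: the general laboratory listing flags values as low or high and by CTCAE grade, so ALP between 3 and 5 x ULN is marked only as high. The general remark about program conventions does not tell a reader which definitions differ.

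**Conclusion.** The point holds as an undeclared mismatch of definitions. The same label covers different limits for 10 of 19 protocol entries, and the SAP does not say so. The practical gap is narrow: three protocol thresholds have no equivalent count (ALP, low glucose, uric acid), and two are covered without being isolated (creatinine above 1.8 x ULN and the hemoglobin fall). The number of subjects affected cannot be derived from the documents, and it may be small. The conclusion rests on the standard conversion factors for glucose and calcium, and on reading the CTCAE summaries as covering the variables in SAP Tables 10-9 and 10-10. It takes no view on which set of limits is right. The correction should be made because the table reports on the primary objective, but no primary or secondary variable changes.

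**What to change.** Reconcile the two sets of tables. In the SAP's markedly abnormal summaries, add rows at the protocol limits for at least ALP, creatinine, low glucose and uric acid (biochemistry) and the hemoglobin fall (hematology), labelled as the protocol definitions. Keep the SAP limits as they are. State that the fall is measured from PA0009 Laboratory Baseline, because SAP 3.3 adopts that baseline after the change of laboratory vendor. A fall that occurred before that first post-entry sample cannot then be counted, and a footnote should say so. State the difference between the two sets of limits and its reason in the SAP, in section 3.10 or beside Tables 10-7 and 10-8.

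The cost is at least five extra rows across two tables (four biochemistry, one hematology) and a short explanatory text. All the analytes are already collected under protocol Table 9-2. The reported counts of markedly abnormal values may be higher.

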**Table 10–9: Definitions of CTCAE grade by hematology parameter**

Parameter (unit)	Definition	Unit	Grade 1	Grade 2	Grade 3	Grade 4
Hemoglobin	Low	g/L	100-<LLN	80-<100	<80	N/A
Hemoglobin	High	g/L	>0-20 above ULN	>20-40 above ULN	>40 above ULN	N/A
Platelets	Low	10  /L	75-<LLN	50-<75	25-<50	<25
WBC	Low	10  /L	3-<LLN	2-<3	1-<2	<1
WBC	High	10  /L	N/A	N/A	>100	N/A
Lymphocytes	Low	10  /L	0.8-<LLN	0.5-<0.8	0.2-<0.5	<0.2
Lymphocytes	High	10  /L	N/A	>4-20	>20	N/A
Neutrophils	Low	10  /L	1.5-<LLN	1.0-<1.5	0.5-<1.0	<0.5

LLN=lower limit of normal, N/A=not applicable; ULN=upper limit of normal; WBC=white blood cell

**Table 10–10: Definitions of CTCAE grade by biochemistry parameter**

Parameter (unit)	Definition	Unit	Grade 1	Grade 2	Grade 3	Grade 4
Creatinine	High	umol/L	>ULN-1.5 x ULN	(>1.5 – 3.0) x ULN	(>3.0 – 6.0) x ULN	>6.0 x ULN
Sodium	Low	mmol/L	130-<LLN	N/A	120-<130	<120
Sodium	High	mmol/L	>ULN-150	>150-155	>155-160	>160
Potassium	Low	mmol/L	3.0-<LLN	3.0-<LLN	2.5-<3.0	<2.5
Potassium	High	mmol/L	>ULN-5.5	>5.5-6.0	>6.0-7.0	>7.0
Calcium	Low	mmol/L	2.0-<LLN	1.75-<2.0	1.5-<1.75	<1.5
Calcium	High	mmol/L	>ULN-2.9	>2.9-3.1	>3.1-3.4	>3.4
Magnesium	Low	mmol/L	0.5-<LLN	0.4-<0.5	0.3-<0.4	<0.3
Magnesium	High	mmol/L	>ULN-1.23	N/A	>1.23-3.30	>3.30
Total cholesterol	High	mmol/L	>ULN-7.75	>7.75-10.34	>10.34-12.92	>12.92

LLN=lower limit of normal, N/A=not applicable; ULN=upper limit of normal.

Note that subjects who meet the decreased potassium criterion of 3.0-<LLN, which is specified as the decreased potassium lab criterion for both CTCAE Grade 1 and Grade 2, will be counted as Grade 2.

The number and percentage of subjects with elevated liver function tests will be presented by treatment group at completion of PA0008 and overall, using on-treatment assessments from all visits in PA0009 (excluding any measurements that occurred prior to the first administration of study medication in PA0009 or more than 140 days after the last administration of study medication) from all visits in PA0009 including those at PA0009 Laboratory Baseline, unscheduled, ET and SFU visits. Each subject will be counted once only. The number and percentage of subjects in the following categories at any time during the study will be presented:

- AST: >3xULN, >5xULN, >8xULN, >10xULN, >20xULN.
- ALT: >3xULN, >5xULN, >8xULN, >10xULN, >20xULN.
- AST or ALT: >3xULN, >5xULN, >8xULN, >10xULN, >20xULN.
- Total bilirubin: >1.5xULN, >2xULN.

The number and percentage of subjects who meet Hy's Law criteria ([Section 10.2.3](#)) will be presented by treatment group at completion of PA0008 and overall, using on-treatment assessments (excluding any measurements that occurred prior to the first administration of study medication in PA0009 or more than 140 days after the last administration of study medication) from all visits including PA0009 Laboratory Baseline, unscheduled, ET and SFU visits. Hy's Law criteria are displayed below:

- (AST  $\geq$ 3xULN or ALT  $\geq$ 3xULN) and Total Bilirubin  $\geq$ 2xULN in the absence of ALP  $\geq$ 2xULN.

To meet the above criterion, a subject must experience the elevation in total bilirubin and ALT or AST and the absence of ALP elevation at the same visit.

All hematology and biochemistry laboratory data (except CRP) will be listed, including age, sex, race, weight, changes from PA0009 Laboratory Baseline for numeric variables, flags for measurements outside the normal ranges, flags for measurements meeting the criteria for each CTCAE grade ([Table 10–9](#) and [Table 10–10](#)), the relative study day, a flag for whether the test was not done and a flag for whether the subject was fasting.

CRP will be listed separately as described in [Section 8](#).

Values that are below the lower limit of the reference range will be flagged as 'L' (low) and values that are above the upper limit of the reference range will be flagged as 'H' (high) in listings. Values that meet the criteria for each CTCAE grade will be flagged as 'LGrx' or 'HGrx' accordingly.

The markedly abnormal laboratory results will be listed separately.

Any additional laboratory assessments performed during the study will be listed separately.

#### **10.4 Potential drug-induced liver injury assessment**

All PDILI events require immediate action, testing, and monitoring. The measurements and additional information required for the assessment of PDILI events when there is a reasonable possibility that they may have been caused by the study medication are included but not limited to those listed in [Table 10–11](#) and [Table 10–12](#).

PDILI laboratory results and additional PDILI information will be listed by treatment group at completion of PA0008 and subject. Where appropriate data will be included in the standard listings as indicated below:

- Family medical history, including any DILI-relevant medical conditions or inheritable disorders, start year and end year (or ongoing if applicable) (presented in the demographics section only for subjects with PDILI events)
- Study medication administration, including the date and time of most recent study medication administration, whether the subject discontinued study medication and the reason

for discontinuation (presented in the compliance and drug concentration data section with a separate listing for PDILI events).

- Blood sample collection for PK including the variable, unit, date and time the sample was taken, and the result (presented in the compliance and drug concentration data section as part of the standard listing).
- Laboratory tests as detailed in Table 10–6 (presented in the laboratory measurements section with a separate listing of PDILI events).
- Vital signs (presented in the safety analysis section as part of the standard listing)
- Lifestyle, including whether the subject has used alcohol in the past 6 months and whether the subject has used illicit drugs in the past 6 months (presented in the demographics section only for subjects with PDILI events).
- Hepatic event medical history, including any medical conditions which could have contributed to the suspected hepatic event prior to study entry will be listed together with all medical history data (presented in the demographics section).
- Symptoms of hepatitis and hypersensitivity, including whether the subject has taken any potentially hepatotoxic medications, whether the subject is experiencing symptoms of hepatitis, and whether the subject is experiencing symptoms of hypersensitivity (presented in the safety analysis section only for subjects with PDILI events).

**Table 10–11: Additional potential drug-induced liver injury information**

New or updated information
Concomitant prescription and over-the-counter medications (eg, acetaminophen, herbal remedies, vitamins); dosages and dates should be included.

Pertinent medical history, including the following:
 
 
• History of liver disease (eg, autoimmune hepatitis, nonalcoholic steatohepatitis or other “fatty liver disease”)
 
• Adverse reactions to drugs
 
• Allergies
 
• Relevant family history or inheritable disorders (eg, Gilbert’s syndrome, alpha-1 antitrypsin deficiency)
 
• Recent travel
 
• Progression of malignancy involving the liver (Note: Metastatic disease to the liver, by itself, should not be used as an explanation for significant AST and/or ALT elevations.)
 

The appearance or worsening of clinical symptoms of hepatitis or hypersensitivity (eg, fatigue, nausea, vomiting, right upper quadrant pain or tenderness, decreased appetite, abdominal pain, jaundice, fever, or rash)

Recent clinically significant hypotension or hypoxemia with compromised cardiopulmonary function
Alcohol and illicit drug use
Results of liver imaging or liver biopsy, if done
Results of any specialist or hepatology consult, if done
Any postmortem/pathology reports

ALT=alanine aminotransferase; AST=aspartate aminotransferase.

